5.1. Efficacy Assessments

Efficacy will be determined by comparing the right and left frontal sinus opening after removal of the stent and dressing on POD 14, and then around day 30, 90, 6 month and 12 months. The frontal sinus opening will be assessed with a rigid endoscope, using 30, 45 and/or 70 degree scopes as necessary. Our primary efficacy outcome will be a grade assigned by 2 blinded, independent sinus surgeon experts as: better, worse or same, comparing overall appearance of the study subject's frontal sinus openings after implant removal.

Additionally, the frontal sinus opening will also be graded on an adhesion/scarring scale, a polypoid edema scale, size in mm of the opening as measured by a visual analog scale/comparison to 4 mm suction, and visualization of the roof of the frontal sinus.

5.2. Safety Assessments

As standard of care for evaluation and management of any CRS patient who has failed medical treatment and is considering surgical treatment, patients will provide information on their general medical and specific rhinologic health. They typically receive a thorough ENT and rhinology focused physical exam. A CT sinus scan will be obtained on all patients as part of standard of care for image guidance during surgery and this will be reviewed in order to confirm inclusion and exclusion criteria prior to surgery. Appropriate SOC surgical screening lab tests as necessary will be reviewed to rule out metabolic, endocrine, inflammatory, autoimmune, and hematologic issues.

For safety assessment, the initial standard of care CRS workup and prior treatments will be documented when the subject enters the study. At each study visit after subjects have undergone a surgical intervention, subjects will be asked about changes to medical and rhinologic health, and in particular if they have had bleeding, eye swelling, change in vision, headaches, nasal discharge or other symptoms since surgery or their last visit.

5.3. Costs to the Subject

Standard costs of office visits, office procedures and surgery will be billed to the subject's insurance. Subjects would be expected to pay standard copayments for office visits and costs incurred through their insurance as described above. These costs could be identical to that which would have been incurred if a subject had not enrolled or withdrawn from the study depending on the patient's insurance. The bioabsorbable steroid eluting implant, if not covered or only partially covered by insurance, may end up costing more than the steroid impregnated nasal dressing. Both randomized dressing materials are currently used as part of standard of care in the

setting of frontal sinus surgery of Draf 2a and 2b types, and costs for both methods of packing/steroid delivery are subject to insurance variability and hence cost to the patients. This would be true of study and non-study patients.

5.4. Payment for Participation

Subjects will not be paid for participating.

5.5. Return of Individual Research Results

Individual research results will not be provided back to subjects.

6. SUBJECT WITHDRAWALS

Subjects will be advised in the written informed consent forms that they have the right to withdraw from the study at any time without prejudice. Subjects will be withdrawn from the research without their consent by the investigator if they no longer qualify for the inclusion/exclusion criteria, are non-compliant (miss required scheduled study visits precluding analysis), or if the investigator determines that it is in the best interest of the subject. There are no additional study activities requiring completion prior to subject withdrawal from the study. Subjects withdrawn from the study will not be replaced.

7. STUDY DEVICES

7.1. Bioabsorbable steroid releasing sinus implant: Propel mini stent ©

7.2. Bioabsorbable steroid releasing sinus implant: Propel contour stent ©

The PI will select which stent to use based on the shape of the post-surgical sinus opening. That is, in some cases the straight mini stent is a better fit, while in others the contour stent better matches the shape of the opening.

7.3. Bioabsorbable nasal dressing impregnated with 2.5 ml of Triamcinolone Acetonide 40 mg/ml: Nasopore ©

The Propel mini/contour stent and the Nasopore nasal dressing with triamcinolone acetonide are commercially available products and approved for use in the nasal sinuses after sinus surgery (see appendix 1-4). It is within standard practice to use these implants after sinus surgery in an attempt to improve mucosal healing and prevent scarring and/or stenosis.

7.4. Subject Enrollment/Randomization

Subjects will be enrolled on the basis of the inclusion and exclusion criteria and signed informed consent. Subjects will be randomized using the envelope method to have either the Bioabsorbable steroid releasing stent placed or Nasopore soaked with 2.5 ml of triamcinolone acetonide 40 mg/ml placed in the left frontal sinus opening. The right frontal sinus opening will

have the other device placed. Patients will serve as their own comparison group and as such there will be a 1:1 ratio of frontal sinus openings treated with each method.

8. RISK/BENEFIT ASSESSMENT

8.1. Potential Risks

- Invasion of subject privacy
- NB The risks of ESS are identical to non-study subjects who received similar procedures
- Theoretical risk of misplacing the stent and piercing the sinus bone.

8.2. Protection Against Risks

Privacy will be protected by minimizing the number people with access to the subject's identifying data, which will be stored in REDCap, making use of its built-in privacy protections. All study personnel will have training in human subject protections.

The risk of misplacing the stent is mitigated by direct imaging of the frontal sinus as the stent is being inserted and by the surgical skill of the surgeon.

8.3. Potential Benefits to Subjects

There is no anticipated benefit to the subject of participating since both stent and dressing treatments are presumed to be equally efficacious.

8.4. Alternatives to Participation

The alternatives to participation in the study include no medical or surgical treatment, continued medical therapy, or standard surgical therapy as deemed clinically indicated by the principal investigator or other treating physician.

9. CONFIDENTIALITY OF DATA AND INFORMATION STORAGE

Information about study subjects will be kept confidential and managed according to the requirements of the Health Insurance Portability and Accountability Act of 1996 (HIPAA). Those regulations require a signed subject authorization informing the subject of the following:

- What protected health information (PHI) will be collected from the subjects in this study
- Who will have access to that information and why
- Who will use or disclose that information
- The rights of a research subject to revoke their authorization for the use of their PHI

In the event that a subject revokes authorization to collect or use PHI, the investigator, by regulation, retains the ability to use all information collected prior to the revocation of subject authorization. For subjects that have revoked authorization to collect or use PHI, attempts should be made to obtain permission to collect at least vital status (i.e. that the subject is alive) at the end of their scheduled study period.

We will exercise the following practices to maintain confidentiality of data and protecting against unauthorized disclosure:

- not downloading identifying information from REDCap except subject ID number (i.e., keep any identifying information separately from any research data)
- locking up research files while they are unsupervised
- using screensavers
- shredding excess copies of paper documents
- protections for codes that link patients to their data
- electronic and physical security of data storage devices and networks
- security measures to protect storage and transmission of electronic data

Quality of life and other questionnaires are routinely acquired for patients during their SOC visits. They are then scanned into the electronic medical record and shredded. Data from these will be abstracted by approved study staff into a REDCap eCRF.

Endoscopic video and images are routinely acquired for frontal sinus patients. The PI transports these from the Clinic to the Medical Center in an AES-256 encrypted hard drive that is unlocked by his thumb print and loaded into DScope, which is hosted on a URMC password-protected server, where they are identified by patient name. The PI and ENT residents have routine access to this video. Video for the study will be edited from this raw footage, first to remove any brief images of the subject e.g. if the scope is moved quickly between nostrils in one take of video. Next it will be edited to standard segments for review and identified with the subject number, side, and time point.

10. RESEARCH INFORMATION IN MEDICAL RECORDS

Study participation will be indicated in the medical record.

11. DATA ANALYSIS AND MONITORING

11.1. Data & Safety Monitoring Plan

I. Overview

A. This is a single center, prospective, observational, minimal risk study performed with a cohort of adult subjects undergoing frontal sinus surgery. Subjects will have SOC surgery and at the end of surgery each nostril will get a dressing or stent that provides mechanical support and also exudes a steroid to aid wound healing. Presently either dressing or stent is typically used in both sinuses at the surgeon's discretion, and this trial will put one of each in each sinus (left/right at random) to compare with each subject as their own control, whether there are noticeable differences in wound healing due to either treatment, during the post-operative course. Subjects will be followed for up to 12 months post-surgery.

B. Adherence statement. The Data and Safety Monitoring Plan (DSMP) outlined below for this study will adhere to the protocol approved by the University of Rochester Research Subjects Review Board (RSRB).

II. Adverse Events

- A. Adverse event assessment
 - a. This is a minimal risk study and there is a risk of loss of privacy and of misplacement of the stent.
 - b. Risk to privacy will be determined by whether identifying subject data had been released. This will be assessed annually.
 - c. Misplaced stent will be determined by whether the stent is correctly in the sinus when it is removed at the post-operative visit when it would normally be extracted.

- B. Adverse event reporting
 - a. Every adverse event that is reported to either the PI or study staff by the subject or other medical staff caring for the subject and which meets the above criteria, or which otherwise merit documentation in the judgement of the PI, will be documented with a description of the event along with a determination by the PI of severity and relatedness to study participation.
 - b. Adverse events will be reported annually to the RSRB as part of their Continuing Review of the study.

III. Safety Review Plan and Monitoring

A. Justification of sample size

The sample size is justified below in section 11.2

B. Safety and study progress reviews

The principal investigator will review adverse events as they occur and annually will review and report to the RSRB on study progress including recruitment and protocol adherence. This annual report will include a list and summary of adverse events, a statement of whether adverse event rates are consistent with pre-study assumptions, a summary of recruitment, and reason for withdrawals.

IV. Informed Consent

Consent is discussed in section 4.2 above.

V. Data Quality and Management

- A. Data collection forms will be completed during and after study visits and transcribed to the REDCap database within a week of the study visit. The PI will review all data collection forms and REDCap on a monthly basis.

- B. The REDCap database is cloud based and backed up by the University of Rochester. It logs data entry and modification and so provides an audit trail if necessary. It also allows compliance of data types during data entry and has other quality control tools to allow the PI to assess the completeness and accuracy of data entry.

VI. Confidentiality

Confidentiality is addressed in section 9, above.

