will have standard post-operative visits at approximately 1 week, 2 weeks, 30 days, 90 days, 6 months and 12 months. On post-operative day 14 the first endoscopic evaluation of the frontal sinus opening after implant removal will be performed. Video is routinely recorded and this will be copied for the study, edited to remove any identifying features of the subjects, for review and scoring by qualified independent reviewers. If at any of the post-operative visits oral steroids, antibiotics or in-office procedures is deemed medically necessary this will be allowed and recorded as part of the study results. Subjects' participation will conclude at the 12 month visit.

Schedule of Activities (R Research/SOC Standard of Care)

Visit	0 (Screening)	Operative Visit	FUV 1	FUV 2	FUV 3	FUV 4	FUV 5	FUV 6
Visit timing	Up to 90 days pre-operative	Day 0	1 week post op (+/-3 days)	2 weeks (+/-5 days)	1 month (28 to 56 days post op)	3 months (+/-14 days)	6 months (+/-21 days)	12 months (+/-21 days)
Obtain informed consent/confirm eligibility (R)	X							
Medical and sinonasal history evaluated (SOC)	X							
Bilateral endoscopic sinus surgery (SOC)		X						
Confirm eligibility/ Randomize treatment (R)		X						
Placement of frontal sinus opening treatments (SOC)		X						
Obtain validated SOC sinonasal symptom and quality of life questionnaires (SOC)	X		X	X	X	X	X	X
Complete ENT and sinonasal exam including rigid endoscopy (SOC)	X		X	X	X	X	X	X
Rigid endoscopy with documentation (SOC)	X	X	X	X	X	X	X	X
Abstraction from endoscopy record on frontal sinus opening scarring, polypoid edema,				X	X	X	X	X

overall condition for data analysis and external review (R)								
Adverse event review (R)			X	X	X	X	X	X

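### Adverse events are rated only for relatedness to study participation; apart from a misplaced stent, attribution to stent or dressing is neither required nor systematic

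*Combined protocol and SAP*

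**What the plan says.** The content of an adverse event record is set in one place, Section 11.1.II.B.a. An event "will be documented with a description of the event", "along with a determination by the PI of severity and relatedness to study participation". The rule covers events "which meets the above criteria, or which otherwise merit documentation in the judgement of the PI". The criteria referred to, in 11.1.II.A, are loss of privacy and stent misplacement. The latter has its own check: "Misplaced stent will be determined by whether the stent is correctly in the sinus when it is removed". The dressing has no counterpart.

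Four other places bear on how the rating will be understood or used:

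- The Schedule of Activities in Section 5 has the row "Placement of frontal sinus opening treatments (SOC", so placement of the devices carries the standard-of-care label. Randomization carries the research label.
- Section 8.1 states "The risks of ESS are identical to non-study subjects who received similar procedures". Its next item is "Theoretical risk of misplacing the stent and piercing the sinus bone".
- Section 5.2 has subjects asked at each post-operative visit "if they have had bleeding, eye swelling, change in vision, headaches, nasal discharge or other symptoms since surgery or their last visit". No side is mentioned.
- Section 11.1.III.B describes an annual report that lists and summarizes events and comments on whether their rates match what was assumed beforehand. No breakdown by device is described.

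Section 7.4 allocates one device to the left frontal sinus opening and the other to the right in every subject.

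**The concern.** In a parallel-group trial, the subject's arm links an event to a treatment even when the event form is silent. Here every subject has both treatments, so that link does not exist. For a local event the only link is the side. The plan uses side for efficacy (Section 9 labels the study video by subject, side and time point) but does not ask for it in the adverse event record.

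The one causal judgement that is required points at study participation, which is not a treatment. For a device labelled standard of care, that category can be read two ways, and neither reading separates stent from dressing. The trial could therefore finish with a list of events from which rates for the stent and for the dressing cannot be built reliably. If side was not noted at the visit, it may not be recoverable later.

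**Working it through.** The plan gives no figure for device-level adverse events, so there is nothing of its own to reproduce. Its sample size (Section 11.2) concerns patency and does not depend on how events are attributed. The check is mainly one of reading.

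**Step 1: does any section require side or device?** Section 11.1.II.B.a requires a description, severity and one relatedness rating. Section 5.2 (visit questions), Section 11.1.III.B (annual report) and Section 11.3 (analysis) add neither side nor device. The answer is no.

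**Step 2: is the relatedness category clear for a device-caused event?**

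- Towards unrelated: the schedule labels device placement standard of care, and Sections 5.3 and 7 describe both products as part of usual practice.
- Towards related: Sections 8.1 and 11.1.II.A list stent misplacement as a risk of the study, the schedule labels randomization research, and 11.1.I says usual practice is the same type of product in both sinuses, whereas the trial places one of each.

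Stent misplacement is clearly inside the category. For any other device effect, two careful raters could differ.

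**Step 3: would a rating of related identify the device?** No. Both devices are in the subject because of participation, so the rating is the same whichever one caused the event.

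**Step 4: what can still be attributed?** A misplaced stent can, by definition. So can a local event whose description happens to name the side, through the left/right allocation in Section 7.4. Other events have no required route to a device.

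**Step 5: illustration of size.** The inputs are 30 subjects (Section 3.1) and an assumed 4 bleeding events, each in a different subject and on one side only. The 4 is hypothetical, because the documents give no bleeding rate. If *k* of the 4 have no recorded side, the count for either device is known only to within *k*, so its rate is known to within *k*/30:

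- *k* = 4 (no description names the side): the stent count lies between 0/30 = 0% and 4/30 = 13.3%. The two-sided 95% Clopper-Pearson upper limit is 1 − 0.025^(1/30) = 11.6% at 0/30 and 30.7% at 4/30. The dressing has the same range.
- *k* = 1: the uncertainty in the rate falls to 1/30 = 3.3 percentage points.
- *k* = 0: each device has one count of events on its side.

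The case *k* = 4 is the worst case. The documents do not say how often a description will name the side.

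**The case against.** A reader might infer that no event can be assigned to either device, that device harm is under-reported by construction, or that the information on side is lost. The documents do not support any of these.

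- A misplaced stent is a named event with its own check and belongs to the stent by definition. A free-text description may name the side, and side identifies the device.
- The statement in Section 8.1 about identical risks concerns the surgery. The next item in that list names the stent risk separately, so 8.1 does not place device harm outside the study. The relatedness wording is ambiguous; it does not exclude device effects.
- The documents do not say that events will be recorded without side, and the event form is not among them. Endoscopy is documented at every follow-up visit, and scarring, polypoid edema and opening size are graded for each opening (Sections 5.1 and 11.3). Much local device effect will therefore be captured by side as efficacy data.
- Side does not establish cause. All subjects have bilateral sinus surgery, so a one-sided bleed may come from the surgery. Headache and systemic steroid effects have no usable side.
- Adverse event rates are neither a primary nor a secondary outcome in Section 11.3.

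All of this stands, and it limits the point. It does not supply a required field for side or device, and it does not make the existing rating able to separate two treatments carried by the same subject. A form may carry more than the protocol asks for, but nothing in the documents ensures it.

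**Conclusion.** The point holds in a limited form. The only required causal rating is against study participation. Its meaning is unclear for device effects other than stent misplacement, and it cannot tell stent from dressing. Beyond the misplaced-stent event, attribution by device is left to the wording of a free-text description. The scheme is also uneven, since the dressing has no named event.

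The size cannot be estimated from the documents. The illustration (0% to 13.3% for either device) rests on an assumed four bleeds and on no description naming the side. It shows the worst case for that count and is not a forecast.

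No planned efficacy analysis is affected. What is at risk is the usefulness of the safety data in a trial whose subjects each carry both treatments. This is a cheap improvement to the record that is worth making; it does not invalidate the design.

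**What to change.** In Section 11.1.II.B.a, replace the single relatedness item with:

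1. Side of the event: left, right, both, or not attributable.
2. Separate relatedness ratings for the stent, the dressing, the surgery and study participation.

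Record side as an observation in its own right, apart from the causal ratings, because those ratings are made by the principal investigator, who under Section 7 also selects the stent.

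In Section 11.1.III.B and in the final analysis under Section 11.3, tabulate events by device side and show non-attributable events in a separate row.

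The cost is four added fields on the event form (side, stent, dressing, surgery; the participation rating already exists) and a few sentences in Section 11. Sample size, visits and treatment do not change. The downside is that headache, systemic steroid effects and events due to the bilateral surgery will often remain non-attributable. The table by side should therefore be presented as a description of where events occurred and not as proof of which device caused them.

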11.2. Sample Size Determination

Sample size is based on a non-inferiority design. Based on historical data it can be estimated that frontal sinusotomy will have a patency (success) rate of 85%. Given the lack of any known evidence to the contrary, we will assume that both the Propel mini/contour stent and the Nasopore impregnated with 2.5 mls of Kenalog 40 mg/ml placed in the FSO after ESS will result in a patency rate of 85%. Given that all prior clinical trials investigating local delivery of steroid to the FSO have utilized the Propel mini or contour stent, this will serve as our “standard therapy” group. Using an $\alpha= 0.05$, Power= 80%, and a minimum significant difference (δ) of 25%, 28 patients (56 total frontal sinus interventions) will be enrolled to be 80% sure that the upper limit of a one-sided 95% confidence interval will exclude a difference in favor of the “standard therapy” group of more than 25%. The ESS surgical procedure typically has a 1% complication rate and frontal sinusotomy failure rate of approximately 5%. Thus by ensuring subjects meet inclusion criteria a) through d) and that none of the exclusion criteria apply prior to enrollment, we would have a very low rate of screen failure, where an enrolled subject does not ultimately meet inclusion criteria e) and f). Hence enrolling 30 subjects should be sufficient to reach our statistical needs.

[figure not shown]
11.3. Planned Statistical Analysis:

Primary outcome measure: Grading by a blinded independent sinus expert as to whether the the propel sinus stent frontal sinusotomy side is better, worse or the same.

[figure not shown]
Secondary outcome measures:

1. Mucosal/polypoid edema
2. Adhesion/scarring
3. Size of frontal sinus opening
4. Visualization of the frontal sinus roof
5. Need for post-operative oral steroids
6. Need for post-operative interventions beyond normal debridement

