2. STUDY DESIGN

2.1. Overview

This is a single center, randomized & controlled trial comparing the efficacy of the Propel mini or contour stent vs. Nasopore impregnated with triamcinolone acetonide at reducing frontal sinus opening stenosis and polypoid edema after ESS in patients with CRS with polyposis. Eligible subjects who undergo standard of care bilateral frontal sinusotomy will have each frontal sinus randomly assigned to either a Propel steroid eluting stent or a Nasopore nasal dressing impregnated with 2.5 ml of triamcinolone acetonide 40 mg/ml. The specific Propel stent will be chosen based on the shape of frontal sinus opening and best fit as decided by the operating surgeon. Patients will be reassessed on approximately post-operative day 7, 14, 30, 90 days, 6 months, and 12 months at their SOC follow-up visits. On the day 14 visit, the frontal sinus Propel stent and Nasopore will be completely removed per SOC. Video will be taken of the frontal sinus opening, and assessed for scarring/adhesions, presence of polypoid edema, frontal sinus patency, need for oral steroids or other interventions. Additionally, endoscopic scoring of frontal sinus by the above measures will be evaluated by 2 independent sinus surgeon reviewers. The reviewers will also be asked to rank the two frontal sinus openings as better, same or worse, compared to the opposite side.

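### Section 11.2 sizes the trial and sets its non-inferiority rule on a patency rate, but the primary outcome is a better/same/worse grade with no stated power or margin

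*Combined protocol and SAP*

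**What the plan says.** Section 11.2 describes a non-inferiority design on a binary outcome. Its starting point is "Based on historical data it can be estimated that frontal sinusotomy will have a patency (success) rate of 85" per cent, assumed for both the stent and the dressing. With α = 0.05, power 80% and δ = 25%, it asks for 28 patients (56 sinuses) "to be 80% sure that the upper limit of a one-sided 95% confidence interval will exclude a difference" of more than 25% in favour of the stent, which is the standard-therapy side. Thirty patients are to be enrolled.

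Section 5.1 defines the primary outcome otherwise: "Our primary efficacy outcome will be a grade assigned by 2 blinded, independent sinus surgeon experts as: better, worse or same". Section 11.3 repeats it with one reader: "Grading by a blinded independent sinus expert as to whether the the propel sinus stent frontal sinusotomy side is better, worse or the same".

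Patency appears in section 2.1, where the video is "assessed for scarring/adhesions, presence of polypoid edema, frontal sinus patency, need for oral steroids or other interventions", and "endoscopic scoring of frontal sinus by the above measures will be evaluated by 2 independent sinus surgeon reviewers". Section 11.3 does not list patency as primary or secondary. The nearest items among its six secondary outcomes are the size of the opening and visualization of the sinus roof.

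On timing, section 5.1 compares the two sides "after removal of the stent and dressing on POD 14, and then around day 30, 90, 6 month and 12 months". On attrition, section 6 states: "Subjects withdrawn from the study will not be replaced".

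**The concern.** The rule in 11.2 needs a success proportion for each side. The grade gives one three-level result per patient. A patient graded same may have two open sinuses or two stenosed ones, and a side graded better may be the better of two open sinuses. The grade therefore cannot be converted into a difference in patency rates.

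Two things are at stake. First, the only decision rule in the readable text cannot be carried out on the primary outcome. If the trial reports non-inferiority of patency, it reports on an outcome that 11.3 does not list; if it reports the grade, it has no criterion for success. Second, the 80% that justifies 28 patients is not the power of the primary analysis.

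Further gaps are provisional, because two figures in sections 11.2 and 11.3 are not shown in the text available. As far as that text goes, the grade has no margin, no rule combines the two readers' grades, and none of the five visits after removal is named primary. Unless the figures supply these, more than one primary result could be reported.

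**Working it through.** **Inputs from section 11.2:** patency p = 0.85 on both sides, margin 0.25, one-sided α = 0.05 (z = 1.645), power 80% (z = 0.842), 28 patients. All other inputs below are assumptions, marked as such.

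**1. The plan's own figure.** With the sides treated as independent,

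n = 2p(1−p)(1.645 + 0.842)² / 0.25² = 0.255 × 6.18 / 0.0625 ≈ 25.2, so 26 patients.

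The Farrington–Manning version, which uses the variance restricted to the margin, gives 28.2. The stated 28 is therefore reproduced for patency. One-sided α = 0.025 would give 33 and does not match.

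**2. Power for patency.** Normal approximation: Φ(0.25/√(2p(1−p)/n) − 1.645). At p = 0.85 and n = 28 this is Φ(0.25/0.0954 − 1.645) = Φ(0.975) = 83.5%. The exact column enumerates all outcomes and applies the Tango score limit. Independent sides are assumed; 80% patency and fewer than 28 pairs are assumptions used to show the range.

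| Evaluable pairs | Patency | Normal | Exact, Tango |
|---|---|---|---|
| 28 | 85% | 83.5% | 81.1% |
| 28 | 80% | 75.6% | 75.0% |
| 26 | 85% | 81.0% | 79.1% |
| 26 | 80% | 72.9% | 72.8% |
| 24 | 85% | 78.2% | 74.6% |
| 24 | 80% | 69.9% | 66.8% |

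Positive within-patient correlation helps: at an assumed 0.2 with 28 pairs, the Tango figures are 86.1% (85% patency) and 81.0% (80% patency).

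**3. Power for the grade.** The documents give no expected split of grades and no margin. For illustration, score the grade +1 (stent better), 0 (same) or −1 (stent worse), carry the 25 points over to P(better) − P(worse), assume no true difference and take one grade per patient. With pd the share graded other than same, the variance of the score is pd, and power = Φ(0.25/√(pd/28) − 1.645).

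- pd = 0.20: Φ(2.958 − 1.645) = 90.5%; exact with Tango limit 86.5%.
- pd = 0.50: Φ(1.871 − 1.645) = 58.9%; exact with Tango limit 60.9%.
- pd = 1.00: Φ(1.323 − 1.645) = 37.4%.

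The one-sided error of the Tango limit at the margin is 4.5 to 5.4% for pd from 0.26 to 0.70, so the exact figures do not rest on an inflated test. The grade formula equals the patency formula only when pd = 2 × 0.85 × 0.15 = 0.255, that is, 74.5% graded same. Nothing in the documents supports that figure.

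**4. Averaging two readers.** If both readers have the same pd and their scores correlate at r, the variance becomes pd(1 + r)/2. By normal approximation with 28 patients:

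| pd | r = 0 | r = 0.3 | r = 0.6 | r = 1 |
|---|---|---|---|---|
| 0.20 | 99% | 98% | 95% | 91% |
| 0.50 | 84% | 75% | 67% | 59% |

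The one-grade figures are thus the full-agreement case (r = 1), the lowest in each row.

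**5. Precision if non-inferiority is dropped.** The two-sided 95% half-width with one grade per patient is 1.96√(pd/28): 0.17 at pd = 0.20 and 0.26 at pd = 0.50.

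**The case against.** The strongest reply has four parts.

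- **The margin can be carried over.** The 25 points can be read on the net-preference scale, as the illustration does, and two averaged readers would raise power well above the one-grade figures. That is right about power: 59% is a lower bound for pd = 0.50, not the expected value. But the documents neither make the transfer nor justify it. Twenty-five points of net preference is a different quantity from 25 points of patency.
- **Patency is not really absent.** Opening size, judged against a 4 mm suction, and roof visualization are secondary outcomes, and the same suction defines an adequate opening at entry. These are related measures, but neither is the binary rate that 11.2 sizes.
- **The missing figures may hold the details.** They could contain a reader rule, a margin or a primary visit, so those points stay provisional. They do not alter the explicit text of 11.2, which sizes on patency, or of 5.1 and 11.3, which name the grade.
- **Attrition is a separate matter.** Section 11.2 allows for about 1% + 5% failures at surgery, and 30 × 0.94 = 28.2 meets its target. That stands; the documents give no dropout rate. The rows with fewer pairs only show what a restated power claim for patency should cover, since withdrawals are not replaced.

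**Conclusion.** The concern holds and must be fixed. The sample size is correct for its own outcome, but that outcome is not the primary one, and the non-inferiority rule cannot be applied to the outcome that is. This rests on explicit text and needs no assumption.

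The trial is not shown to be underpowered. Power for the grade is unstated, and under the borrowed margin it could be above or below 80%, depending on the share graded same and on how far the two readers agree. The missing margin, reader rule and primary visit are provisional on the figures not shown. The one-reader wording in 11.3 conflicts with the two readers in 2.1 and 5.1 whatever those figures contain.

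**What to change.** Name one primary visit, make the others secondary, correct 11.3 to two readers, and take one of three routes.

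- **(a) Keep the grade, for non-inferiority.** Score it +1, 0, −1 for the stent side and average over the two readers. State and justify a margin on that scale and name the interval method. Replace the 80% in 11.2 with power over a range of same rates and reader agreement.
- **(b) Make patency primary.** Use the item the two readers already score. The investigators write its definition and the rule for disagreement in advance. Analyse stent minus dressing as a paired difference in proportions, for example with a Tango score interval, against the 25 points. Make the grade the first secondary outcome. State that 80% holds for 28 evaluable pairs at 85% on both sides with no negative within-patient correlation, and add the range: about 75% at 80% patency, and 75 to 78% with 24 pairs at 85% (independent sides).
- **(c) Keep the grade, as a difference comparison.** Use the same averaged score with a two-sided 95% interval and its expected width. Remove the non-inferiority claim and the 80% for the primary outcome.

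The cost is an amendment to 5.1, 11.2 and 11.3, with no added patients, visits or readers. It is more than editing: (a) needs a justified margin, (b) changes the primary outcome and needs a definition, and (c) gives up the non-inferiority claim. The stated power may become less favourable. The choice should be fixed before any grades are compared by treatment.
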